12.1.5.1. Visit 5 (Day 21 [\pm 3 days])

Subjects will return to the clinic on Day 21 (\pm 3 days), at which time the following procedures will be performed:

1. Collect blood sample for plasma MDGN-002 concentration and PK analysis

2. Assess and record any AEs and concomitant medications
3. Review diary completion
4. Assess subject response and available results against individual stopping rules criteria defined in [Section 8.5.1](#).

In addition, ongoing AEs from the previous visit will be assessed and any change in their status will be recorded.

12.1.5.2. Visit 6 (Day 28 [\pm 3 days])

Subjects will return to the clinic on Day 28 (\pm 3 days), at which time the following procedures will be performed prior to dosing:

1. Perform a complete physical examination, including measurement of weight
2. Collect vital signs, including systolic and diastolic blood pressures, pulse, respiration rate and temperature
3. Perform 12-lead ECG
4. Collect blood sample for clinical laboratory tests
5. Collect blood samples for plasma MDGN-002 concentration, PK and ADA analyses
6. Collect blood sample for exploratory analyses as defined in [Table 1](#)
7. Collect stool for fecal calprotectin analysis
8. Collect urine sample for urinalysis
9. Collect urine sample for urine β -hCG test (for females of childbearing potential only)
10. Administer the CDAI (CD only)
11. Review diary completion
12. Assess and record concomitant medication use and any newly occurring AEs since the last evaluation

In addition, ongoing AEs from the previous visit will be assessed and any change in their status will be recorded.

After completing these assessments, subjects will receive MDGN-002 by SQ injection in the abdomen in a zone of 4 to 10 cm from the umbilicus with the injection site rotated with each subsequent dose. Vital sign assessments will be conducted within 60 minutes post-dosing.

Subjects will remain in the clinic for 60 minutes after the investigational product has been administered. During this time, the following details will be recorded:

1. Any AEs occurring after dosing
2. Any concomitant medications administered after dosing.

NOTE: Stool samples may be obtained at any time during the visit

3. Assess subject response and available results against individual stopping rules criteria defined in [Section 8.5.1](#).

After completion of the post-dosing assessments, the subject may leave the clinic.

12.1.5.3. Visit 7 (Day 35 [\pm 3 days])

Subjects will return to the clinic on Day 35 (\pm 3 days), at which time the following procedures will be performed:

1. Collect blood sample for pharmacokinetic analysis
2. Assess and record any AEs and concomitant medications
3. Review diary completion
4. Assess subject response and available results against individual stopping rules criteria defined in [Section 8.5.1](#).

In addition, ongoing AEs from the previous visit will be assessed and any change in their status will be recorded.

12.1.5.4. Visit 8 (Day 42 [\pm 3 days])

Subjects will return to the clinic on Day 42 (\pm 3 days), at which time the following procedures will be performed prior to dosing:

1. Perform a brief physical examination, including measurement weight
2. Collect vital signs, including systolic and diastolic blood pressures, pulse, respiration rate and temperature
3. Collect blood sample for clinical laboratory tests
4. Collect blood sample for plasma MDGN-002 concentration and PK analysis
5. Administer the CDAI
6. Review diary completion
7. Assess and record any AEs and concomitant medications

In addition, ongoing AEs from the previous visit will be assessed and any change in their status will be recorded.

After completing these assessments, subjects will receive MDGN-002 by SQ injection in the abdomen in a zone of 4 to 10 cm from the umbilicus with the injection site rotated with each subsequent dose. Vital sign assessments will be conducted within 60 minutes post-dosing.

Subjects will remain in the clinic for 60 minutes after the investigational product has been administered. During this time, the following details will be recorded:

1. Any AEs occurring after dosing
2. Any concomitant medications administered after dosing.
3. Assess subject response and available results against individual stopping rules criteria defined in [Section 8.5.1](#).

After completion of the post-dosing assessments, the subject may leave the clinic.

12.1.5.5. Visit 9 (Day 49 [\pm 3 days])

Subjects will return to the clinic on Day 49 (\pm 3 days), at which time the following procedures will be performed:

1. Collect blood sample for plasma MDGN-002 concentration and PK analysis
2. Assess and record any AEs and concomitant medications
3. Review diary completion

In addition, ongoing AEs from the previous visit will be assessed and any change in their status will be recorded

12.1.5.6. Visit 10 (Day 56 [\pm 3 days])

Subjects will return to the clinic on Day 56 (\pm 3 days), at which time the following procedures will be performed:

1. Perform a complete physical examination, including measurement of weight
2. Collect vital signs, including systolic and diastolic blood pressures, pulse, respiration rate and temperature
3. Perform 12-lead ECG
4. Collect blood sample for clinical laboratory tests
5. Collect blood samples for plasma MDGN-002 concentration, PK and ADA analysis
6. Collect blood sample for exploratory analyses as defined in [Table 1](#)
7. Collect stool for fecal calprotectin analysis
8. Collect urine sample for urinalysis
9. Collect urine sample for urine β -hCG test (for females of childbearing potential only)
10. Administer the CDAI (CD only)
11. Review diary completion
12. Administer IBD-Q questionnaire
13. Conduct the endoscopy and biopsy
14. Calculate the Modified Mayo Score (excluding the PGA component) using the endoscopy score from the central reader and the diary data on stool frequency and rectal bleeding (UC only)
15. Assess and record any AEs and concomitant medications
16. Assess subject response and available results against individual stopping rules criteria defined in [Section 8.5.1](#).

In addition, ongoing AEs from the previous visit will be assessed and any change in their status will be recorded.

NOTE: Stool samples may be obtained at any time during the visit.

12.1.6. Early Termination

If a subject is withdrawn from the study for any reason, every effort must be made to conduct all Day 56 (Visit 10) procedures and assessments (see [Section 12.1.5.6](#)).

12.1.7. Safety Follow-Up

12.1.7.1. Visit 11 (Day 84 [± 3 days])

Subjects will return to clinic 28 days (± 3 days) after Visit 10 or the early termination visit for a safety follow-up visit, as appropriate. Subject will have blood collected for plasma MDGN-002 concentration, PK and ADA analyses. Any concomitant medications and newly occurring AEs since the last visit will be recorded. In addition, ongoing AEs from the previous visit will be assessed and any change in their status will be recorded.

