^c After Day 0 (Visit 2), visits at which MDGN-002 is administered should occur every 14 ± 3 days. These visits should be scheduled relative to Day 0 (Visit 2), which is the baseline visit.

^d Medical history will include details regarding all UC/CD-related surgical procedures and hospitalizations.

^e A complete physical examination will be performed at Visits 1, 2, 6, and 10/ET. Brief physical examinations will be done at Visits 4 and 8. Height will be measured at V2 only.

^f Vitals will be taken pre-and post-dose on Visit 2, 4, 6 and 8. Post-dose vitals should be taken at least 60 minutes post-dose, immediately prior to discharge.

^g TB testing will include QuantiFERON-TB Gold (QFT) blood testing or PPD skin testing. If the subject's PPD tine skin test is ≥ 5 mm, a chest x-ray will also be employed for TB assessment.

^h Clinical laboratory assessments at Visits 1, 6, and 10/ET include: CBC with differential, hematology, serum albumin, CRP, liver panel, GGT. Anti-drug antibodies will be measured at Visits 2, 6 and 10. Clinical laboratory assessments at Visits 2, 4, and, 8 include hematology and serum albumin.

ⁱ Pre-dose PK blood samples will be obtained within 60 minutes prior to dose at Visits 2, 4, 6 and 8.

^j Exploratory analyses will examine LIGHT, cytokines, RNA sequencing, and flow cytometry.

^k Serum β -hCG will be conducted at Visit 1 and Urine β -hCG tests will be conducted on Visits 2, 6 and 10.

^l Screening for amphetamines, barbiturates, benzodiazepines, cocaine, opiates, phencyclidine, cannabinoids, propoxyphene, and methadone as warranted.

^m Stool samples will be obtained at Visits 1, 6 and 10/ET. C.difficile test will be performed only at Visit 1. Fecal calprotectin will be measured at all specified visits.

ⁿ Histological confirmation of disease is performed only at Visit 1. Documentation will be provided to site for confirmation or prior documentation of histological confirmation is acceptable. Exploratory biomarker histology will be completed for samples provided to study central laboratory provider.

^o Adverse event monitoring begins at the time informed consent is signed.

^p Subjects will be required to remain in the clinic for at least 60 minutes after MDGN-002 administration for adverse event monitoring.

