10. TREATMENT OF SUBJECTS

10.1. Description of Investigational Product

A description of the investigational product is provided in [Section 11.1](#)

Subjects in each dose cohort will receive the investigational product as a single SQ injection in the abdomen in a zone of 4 to 10 cm from the umbilicus with the injection site rotated with each subsequent dose. The dose of MDGN-002 will be administered on Days 0, 14, 28, and 42. After Day 0, injections must occur within \pm 3 days of the scheduled 14-day intervals.

Subjects in the first dose cohort will receive MDGN-002 1.0 mg/kg for the entire 8-week, open-label treatment period. Data from this cohort will be reviewed by the Data Monitoring Committee as described in [Section 8.4](#) before subjects in the second dose cohort can be treated.

Eligible subjects in the second dose cohort will receive MDGN-002 3.0 mg/kg for the entire 8-week, open-label treatment period. Data from the second cohort will be reviewed, as described in [Section 8.4](#), after all subjects have completed the treatment period and its associated assessments.

Any quality issue noticed with the receipt or use of an investigational product provided by the sponsor (deficiency in condition, packaging, appearance, pertaining documentation, labeling, expiration date, etc.) should be promptly communicated to the sponsor, who will investigate.

A potential defect in the quality of investigational product provided by the sponsor may be subject to initiation of a recall procedure by the sponsor. In this case, the investigator will be responsible for promptly addressing any request made by the sponsor, in order to recall the investigational product and eliminate potential hazards.

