12.3.1.5.8. Evaluation of Laboratory Values

The normal ranges of values for the clinical safety laboratory assessments will be provided by the responsible laboratory and submitted to Aevi Genomic Medicine, LLC prior to the beginning of the study. They will be regarded as the reference ranges upon which clinical decisions will be made.

If a laboratory value is out of the reference range, it is not necessarily clinically relevant, with the exception of those defined as exclusionary per [Section 9.2](#). The investigator must evaluate the out-of-range values and record his/her assessment of their clinical relevance in the appropriate eCRF.

All laboratory values which, in the investigator's opinion, show clinically relevant or pathological changes during or after termination of the treatment are to be discussed with the medical monitor and reported as AEs and followed, as described in [Section 12.3.1.6.2](#).

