5.3 NUMBER OF DAYS EXPOSED TO STUDY DRUG

Based upon the pharmacokinetics of the drug (t1/2 of 18.0 to 27.0 days), each dose will count as 14 days of exposure to investigational product. Therefore, days of exposure to study drug will be calculated as:

• (last dose date – first dose date + 14).

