9.3 CLINICAL LABORATORY EVALUATIONS

Clinical laboratory tests (hematology, serum chemistry, fecal chemistry, and LIGHT [serum and tissue]) will be summarized from baseline through Visit 10/ET by visit. For each individual lab test value, the observed value and change from baseline will be summarized by disease and cohort.

All results, along with urinalysis and other laboratory tests, will be listed.

Other laboratory tests include cytokines (e.g. IL-1 beta, IL-6, IL-8, and TNF-alpha, and other exploratory cytokines), flow cytometry analysis of peripheral blood leukocytes, and RNA sequencing.

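### Scheduled haematology and chemistry end at Day 56, with about 31–44% of the drug given still to be eliminated; the safety follow-up visit draws blood only for concentration/PK and ADA

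*Protocol*

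**What the plan says.** Dosing is fixed in Protocol 10.1: "The dose of MDGN-002 will be administered on Days 0, 14, 28, and 42".

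Protocol Table 1, footnote h, sets the laboratory schedule: "Clinical laboratory assessments at Visits 1, 6, and 10/ET include: CBC with differential, hematology, serum albumin, CRP, liver panel, GGT", and "Clinical laboratory assessments at Visits 2, 4, and, 8 include hematology and serum albumin". The clinical laboratory row of Table 1 has no entry after Visit 10.

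For the safety follow-up, Protocol 12.1.7.1 (Visit 11) states: "Subject will have blood collected for plasma MDGN-002 concentration, PK and ADA analyses". Otherwise the visit records AEs and concomitant medication. SAP 9.3 matches this: the laboratory tests "will be summarized from baseline through Visit 10/ET by visit".

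AE collection runs longer. Protocol 12.3.1.6.2 collects AEs from consent to the final safety follow-up visit. SAP 9.2 summarises treatment-emergent AEs through Visit 11 for subjects who complete the study.

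Protocol 8.5.1 and 8.5.2 list low white cell, neutrophil and platelet counts, ALT/AST thresholds and Hy's Law among the stopping criteria. SAP 5.3 gives the half-life: "Based upon the pharmacokinetics of the drug (t1/2 of 18.0 to 27.0 days), each dose will count as 14 days of exposure".

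**The concern.** The primary objective is safety and tolerability. Several events that the protocol treats as important enough to stop a subject or the study are defined by a blood test. Protocol 8.5.1 itself provides for an ALT or AST above three times the upper limit without symptoms, so it recognises that such signals can be silent. Asking about AEs at Visit 11 cannot find them.

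The AE window therefore closes at Visit 11 and the laboratory window at Day 56, while the SAP's half-life implies substantial drug still in the body. A study report could show no late laboratory toxicity simply because no test was scheduled.

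There is a second, conditional consequence. Escalation may proceed once Cohort 1 has reached Visit 4 and the committee has reviewed the data (Protocol 8.1, 8.4), and the UC subjects enrol after escalation. One subject's Day 56 to 84 period may thus overlap another's dosing. The study-level rules in 8.5.2 act on as few as one or two subjects, so with about 14 in all, one unobserved event could count.

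**Working it through.** **1. Is the gap real, or a gap in the extracted table?** Table 3 settles it. Volume times number, summed over its rows, gives 12.0 + 21.0 + 4.0 + 18.0 + 10.0 + 9.0 + 7.5 + 10.5 + 6.0 + 6.0 = 104.0 mL, the stated total. The sample counts then show which visits are covered:
- Haematology 6 and chemistry 6: Visits 1, 2, 4, 6, 8 and 10. None is left for Visit 11.
- PK after Day 0, 9 samples: Visits 3 to 11 (Protocol 12.3.2.1). Visit 11 is included.
- ADA, 5 samples: Visits 2, 4, 6, 10 and 11 (SAP 11). Visit 11 is included.

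Table 1, footnote h, 12.1.7.1, Table 3 and SAP 9.3 all agree.

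**2. The SAP's own exposure figure.** Last dose date minus first dose date plus 14 is 42 − 0 + 14 = 56 days. Counted exposure thus ends on the day of the last laboratory test. The documents give no figure for drug remaining then.

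**3. Laboratory cover after the last dose, in half-lives.** Day 56 − Day 42 = 14 days; 14/27 = 0.52 and 14/18 = 0.78.

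**4. Drug remaining.** Inputs are four equal doses on Days 0, 14, 28 and 42 (Protocol 10.1) and "t1/2 of 18.0 to 27.0 days" (SAP 5.3). First-order elimination and immediate, full absorption are assumed. The amount at day T, in single doses, is the sum of 2^(−(T − d)/t½) over the dose days d; dividing by 4 gives the share of all drug given.

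At Day 56:
- t½ = 18: 0.583 + 0.340 + 0.198 + 0.116 = 1.238 doses; /4 = 30.9%.
- t½ = 27: 0.698 + 0.487 + 0.340 + 0.238 = 1.763 doses; /4 = 44.1%.

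| Day | Doses, t½ 18 d | Share | Doses, t½ 27 d | Share |
|---|---|---|---|---|
| 42, just after dose 4 | 2.122 | 53.0% | 2.526 | 63.1% |
| 56 | 1.238 | 30.9% | 1.763 | 44.1% |
| 70 | 0.722 | 18.0% | 1.231 | 30.8% |
| 84 | 0.421 | 10.5% | 0.859 | 21.5% |

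Under linear kinetics the same shares apply to the AUC still to come. Laboratory cover to Day 56 therefore takes in 55.9% to 69.1% of total exposure; cover to Day 84 would take in 78.5% to 89.5%.

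**5. Sensitivity at Day 56.** With an assumed absorption half-life of 2 to 5 days (not in the documents), the share still to be eliminated is 35% to 53%. With the fourth dose and Visit 10 at opposite ends of their ±3-day windows, it is 26% to 37% for 18 days and 40% to 49% for 27 days. The lowest value in any of these is 26%.

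**6. When is the follow-up visit?** Protocol 8.2.3 and 12.2 put it 28 days after the final dose: 42 + 28 = Day 70. Protocol 12.1.7.1 puts it 28 days after Visit 10 or the early termination visit: 56 + 28 = Day 84 for a completer. Section 8.1 contains both versions. A test at that visit would fall with 18% to 31% of the drug remaining on the first reading and 10.5% to 21.5% on the second.

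**The case against.** The strongest case for the plan is that residual drug is not residual risk. On the same model the amount peaks just after the Day 42 dose at 2.12 to 2.53 doses. By Day 56 it is down to 58% to 70% of that peak (1.238/2.122 and 1.763/2.526), and it only falls afterwards. Haematology on Days 0, 14, 28, 42 and 56 covers the whole rise and two weeks beyond the peak. Nothing legible points to late laboratory toxicity: Protocol 8.3 lists only injection site reactions as a preclinical observation, and 12.3.1.6.7.1 names no event of special interest. The non-clinical and clinical data sections (6.2.2, 6.2.3) cannot be read, so a justification may sit there. All of this stands: the 31–44% describes exposure and says nothing about how likely a late event is.

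A reader might infer that late cytopenias or liver injury would simply go undetected. The documents do not support that. Visit 11 is in clinic and records AEs, AEs are followed to closure (12.3.1.6.2), and SAP 5.8 allows for unscheduled laboratory assessments. What escapes is narrower: a new, asymptomatic abnormality arising after Day 56. Nothing requires an unscheduled test to look for it, and post-baseline unscheduled results are only listed.

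A reader might also see a contradiction with Protocol 12.3.1.5.8, under which laboratory values that "show clinically relevant or pathological changes during or after termination of the treatment are to be discussed with the medical monitor". There is none. Early-termination samples, and Visit 10 samples taken 14 days after the last injection, can already be post-treatment values.

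Finally, dosing ends on Day 42 and escalation is decided after Visit 4, so a Visit 11 result cannot stop that subject's dosing and is not required for escalation. That too stands. It leaves the study-level rule, and only if others are still being dosed; the documents give no enrolment timeline from which to judge the overlap.

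**Conclusion.** The point holds as a gap in safety characterisation that is cheap to close. It is neither an internal contradiction in the laboratory schedule nor evidence of an unrecognised hazard. The absence of scheduled haematology and chemistry after Visit 10 is certain. The 31–44% rests on the SAP's half-life range, equal doses on the planned days, first-order elimination and immediate, full absorption; slower absorption raises it, and visit windows move it between 26% and 49%. No late-event rate can be estimated from the documents.

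Two related matters need reconciling. The first is the timing of the follow-up visit, together with SAP 9.2, which ends the treatment-emergent AE summary 28 days after the last dose for subjects who discontinue, whereas 12.1.7.1 places their Visit 11 28 days after the early termination visit. A laboratory AE first found at that visit could fall outside the summary. The second is liver testing: footnote h places the liver panel at Visits 1, 6 and 10 only, while Table 3 budgets six chemistry samples. Albumin alone may account for the other three, but the documents do not say whether liver enzymes are run at Visits 2, 4 and 8.

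**What to change.** - In Protocol 12.1.7.1 and Table 1, add the existing haematology and serum chemistry tubes, including the liver tests, to the Visit 11 draw.
- In Table 3, raise the haematology and chemistry counts from 6 to 7 each. The added volume is 2.0 + 3.5 = 5.5 mL, taking the total from 104.0 to 109.5 mL.
- In SAP 9.3, extend the laboratory summary period to Visit 11.
- In the same edit, reconcile the follow-up timing across Protocol 8.1, 8.2.3, 12.2 and 12.1.7.1 and the SAP 9.2 cut-off for subjects who discontinue, and reconcile the liver-panel visits in footnote h with the six chemistry samples in Table 3.

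The cost is 5.5 mL of blood and one standard panel per subject, for about 14 subjects, at a draw already scheduled. No visit is added, and no dose or stopping rule changes. If the follow-up visit is at Day 84, scheduled laboratory cover after the last dose rises from 14 to 42 days (42/27 = 1.56 to 42/18 = 2.33 half-lives).

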12.2. Study Duration

The overall study duration is expected to be approximately 26 weeks (including up to 14 weeks of screening [inclusive of wash-out of up to 12 weeks, if required], 56 days of open-label treatment, and a follow-up visit approximately 28 days after the final dose of investigational product).

The planned sequence and maximum duration of the study periods will be as follows:

1. Screening period: approximately 2 weeks
2. Wash-out period, if applicable: Up to 12 weeks from the subject's last dose of biological treatment
3. Open-label treatment period: 56 days (beginning on Day 0 with doses administered q14 days)
4. Follow-up: 28 days after the last dose of investigational product.

The maximum study duration for each subject is approximately 26 weeks.

The maximum treatment duration for each subject is approximately 56 days, with SQ injections beginning on Day 0 and continuing every 14 (± 3) days through Day 42.

Note: Extensions of the screening window to accommodate clinical laboratory re-testing timeframes (excluding endoscopy with biopsy) are permitted as agreed with medical monitor.

12.3. Assessments

12.3.1. Safety Assessments

Safety assessments will include monitoring of AEs, clinical laboratory tests, vital signs measurements, physical examinations (including measurement of weight) and 12-lead ECG parameters, as described below. Demographic information and medical and medication histories will be obtained at the screening visit.

All safety assessments are to be recorded on the appropriate eCRF.

The Investigator's Brochure is the reference document for safety information pertaining to this study and is provided under separate cover.

